3.3 Inclusion of Women and Minorities

The study is open anyone regardless of gender or race/ethnicity. Efforts will be made to extend the accrual to a representative population, but in a trial which will accrue approximately 43 subjects, a balance must be struck between subject safety considerations and limitations on the number of individuals exposed to potentially toxic or ineffective treatments on the one hand and the need to explore gender, racial, and ethnic aspects of clinical research on the other. If differences in outcome that correlate to gender, racial, or ethnic identity are noted, accrual may be expanded or additional studies may be performed to investigate those differences more fully.

4.0 SCREENING AND REGISTRATION PROCEDURES

4.1 Screening Procedures

Diagnostic or laboratory studies performed exclusively to determine eligibility for this trial will be done only after obtaining written informed consent. Studies or procedures that were for clinical indications (not exclusively to determine study eligibility) may be used for baseline values, even if the studies were done before informed consent was obtained. Reference is made to Section 10.0 – Study Calendar.

4.2 Informed Consent

The investigational nature and objectives of the trial, the procedures and treatments involved and their attendant risks and discomforts, and potential alternative therapies will be carefully explained to the subject and a signed informed consent will be obtained. Documentation of informed consent for screening will be maintained in the subject's research chart and medical record and the patient will receive a copy of the signed informed consent document. All Institutional, Federal, and State regulations concerning Informed Consent will be fulfilled.

4.3 Registration Requirements/Process

Confirming and reserving a slot

Eligible subjects will be registered on the study centrally by the Data Coordinating Center (DCC) at City of Hope. Staff (including physicians, protocol nurses and/or CRCs) should call the DCC at [contact], [name] to verify the current dose level and slot availability, and to reserve a slot for a specific prospective subject. Slots can only be held for a limited time.

Eligible subjects must be registered **prior** to start of protocol therapy. Issues that would cause treatment delays should be discussed with the Principal Investigator. If a subject does not receive protocol therapy following registration, the subject's registration on the study may be canceled after discussion with the PI. The Data Coordinating Center should be notified of cancellations as soon as possible.

Registration Process – City of Hope Subjects

Once a slot at a dose level has been reserved, the signed informed consent has been obtained, all pretreatment evaluations have been performed, and subject's eligibility has been confirmed by the Data Coordinating Center, a subject will be registered on study.

To register a subject, the treating physician should contact the protocol nurse or the responsible Clinical Research Coordinator (CRC) in the Clinical Trial Office (CTO) to complete the eligibility checklist.

The protocol nurse or CRC will contact the Data Coordinating Center at City of Hope [contact], [name] or via e-mail at [contact]), scan and EMAIL a copy of the completed and signed eligibility checklist, a copy of the signed Informed Consent (including a copy of signed subject's bill of Rights and HIPAA authorization form) and copies of any required pre-study test results that are not readily available in the COH electronic medical record to [contact].

The protocol nurse or CRC may then call the Data Coordinating Center [contact] [name]) to confirm receipt of all registration documents. To complete the registration process, the Data Coordinating Center will:

- Verify and confirm the subject's eligibility.
- Assign a subject accession number (for example, COH-001, COH-002, etc.).
- Register the subject on study centrally (the City of Hope CRC assigned to the trial will still be responsible for accessioning via MIDAS).
- Assign the subject to a dose level (as applicable).
- Complete and email a Confirmation of Registration form within 24 hours to include the COH subject study number and dose level to the study team, which will include the Principal Investigator, treating physician, protocol nurse, CRC and COH IDS Pharmacy.
- Call the protocol nurse and/or CRC to verbally confirm registration.
- Enter the subject into Medidata RAVE.
- A subject failing to meet all protocol requirements will not be registered.

Patients must begin protocol treatment within 1 week following registration.

4.4 Screen Failures and Registered Participants Who Do Not begin Study Treatment

The reason for screen failure or failure to begin treatment for registered participants will be documented.

4.5 Dose Level Assignment

During the phase I portion of the trial, participants will be assigned to the dose level that is currently open. Participants in the phase II portion of the trial will initiate study agent at the recommended phase II dose level.

5.0 TREATMENT PROGRAM

5.1 Treatment Overview

This is a Phase I/II, open label, non-randomized, dose escalation study to determine the MTD, safety, preliminary efficacy and pharmacokinetics and pharmacodynamics of 8-Cl-A administered as a 4 hour intravenous infusion daily for 5-days every 4 weeks in patients with relapsed/refractory AML. Participants will receive up to four cycles of treatment. Participants will be hospitalized during treatment administration (at minimum the first 6 days of the cycle). Participants will be admitted to the telemetry unit and undergo continuous cardiac monitoring from start of treatment until 24 hours after completion of therapy during Cycles 1-4.

Participants who end study treatment for reasons other than disease progression will undergo active follow-up (Section 5.9) per institutional SOP for response assessment until disease progression or the initiation of a new therapy. All participants will be followed for survival (Section 5.9).

For a detailed tabular view of the treatment, monitoring, and follow-up schedule, see the Study calendar in Section 10.

5.2 Treatment cycle definition

Participants will be treated in 28-day treatment cycles until disease relapse, progression, unacceptable toxicity, withdrawal of consent, or other protocol specified parameters to stop treatment.

Once a treatment cycle has began (i.e. the Day 1 dose administered) if there is a hold in administering the study agent (see section 6.3.2), **missed doses may be made up if the criteria to resume treatment are met within 48 hours, or by Day 5 of the treatment cycle, whichever is later**. Otherwise missed administrations will not be made up, and treatment will resume with the next cycle (assuming start of cycle criteria are met). Should a hold or delay in treatment occur, after the last dose is administered in a given cycle, there will be a 21 day break, which may result in a delay in the start of the subsequent cycle.

5.3 Phase I Treatment Plan

The phase I trial will implement a 3+3 dose escalation, de-escalation design to ensure safety and to allow for the evaluation of toxicities associated with 8-chloro-adenosine. See Section 13.3 for dose escalation/de-escalation rules, and Section 13.2 for the definition of DLT.

For this single agent phase I trial, up to four dose levels ('a' levels) of 8-chloro-adenosine will be considered if the accelerated stage is maintained throughout. The first cohort will start at dose level 1a. Intermediate dose levels, in increments of 50% from the planned four dose levels, will be explored in the presence of dose limiting toxicity or unacceptable moderate toxicity (see Section 13.2). Intermediate dose levels ('b' levels) are defined as follows: 150mg/m²; 300 mg/m²; and 600 mg/m².

Table 5.3.1 Phase I Dose Levels

Dose Level	8-Chloro-Adenosine Dose
-1	50 mg/m ² Days 1-5 of a 28 day cycle
1a	100 mg/m ² Days 1-5 of a 28 day cycle
1b	150 mg/m ² Days 1-5 of a 28 day cycle
2a	200 mg/m ² Days 1-5 of a 28 day cycle
2b	300 mg/m ² Days 1-5 of a 28 day cycle
Starting dose with amendment v07	400 mg/m² Days 1-5 of a 28 day cycle
3b	600 mg/m ² Days 1-5 of a 28 day cycle
4a	800 mg/m ² Days 1-5 of a 28 day cycle

There will be no intra-patient dose escalation; participants will undergo dose modification due to toxicity per Section 6.3.

5.4 Phase II Treatment Plan

Following the phase I trials described above, a single arm phase II study will be conducted where the recommended phase II dose (RP2D) is brought forward for activity evaluation.

There will be no intra-patient dose escalation; participants will undergo dose modification due to toxicity per Section 6.3.

5.5 Agent Administration

8-Chloro-adenosine will be administered as an intravenous infusion daily for the first 5 days of each cycle, based on the BSA calculated from the weight measurement taken on Day 1 of the treatment cycle. See Section 8.1.4 for agent preparation. 8-chloro-adenosine will be infused over 4 hours +/- 10 minutes. The infusion rate should not exceed 500 ml/hr. Infusion line will be flushed with 5% dextrose after completion of infusion. Infusion is to be completed within 12 hours of agent preparation during which time it should be stored at room temperature.

Start of cycle criteria are listed in Section 6.2.

Dose levels for dose modification are detailed in Table 5.3.1. There will be no intra-patient dose escalation; participants will undergo dose modification due to toxicity per Section 6.3.2.

5.6 Study Procedures

For a detailed list of all study procedures including timing and windows, see Section 10.

5.7 Duration of Therapy & Criteria for Removal from Study Treatment

Duration of therapy will depend on individual response, evidence of disease progression and tolerance, or completion of 4 cycles of study treatment. Patients may continue for up to 4 cycles of treatment unless unacceptable toxicity or disease relapse/progression. In the absence of treatment delays due to adverse events, treatment may continue until one of the following criteria applies:

- Participant demonstrates disease progression.
- Intercurrent illness that prevents further administration of treatment
- Unacceptable adverse event(s) (see Section 13.2, 6.3.1)
- Participant withdraws from the treatment phase of the study
- General or specific changes in the participant's condition that render the participant unacceptable for further treatment in the opinion of the treating investigator.

Documentation of the reason for discontinuing therapy and the date effective should be made in the medical record and appropriate eCRF. The participant should then proceed to off-treatment procedures for safety monitoring and follow-up procedures. The participant status is to be modified in the MIDAS system once the off-treatment period is completed. Alternative care options will be discussed with the participant.

5.8 End of Treatment Evaluations

All participants will be followed until resolution or stabilization of any serious adverse events occurring during treatment or starting within 30 days of last study drug or completion of the Day 30 End of Treatment assessments. See Section 10 for a list of all assessments and windows.

5.9 Active Follow Up and Survival Follow Up

Participants who do not progress while on treatment will be in *Active Follow Up*, where they will continue to undergo response assessment until disease progression, the initiation of a new therapy or for a maximum of 2 years after their first dose of study agent.

Participants who progress during Treatment Phase skip *Active Follow-Up* phase and continue directly into *Survival Follow-up* phase.

In *Survival Follow-Up* participants will be followed for survival information for a maximum of 2 years after their first dose of study agent. This may be obtained by reviewing the City of Hope medical record,

contacting the participant and/or review of outside medical records. Note: This is not intended to be an all inclusive list.

The schedule and windows for assessments and data collection points are further detailed in Table 10.

5.10 Criteria for Completion of Study Participation

Participants will be followed until disease progression, unacceptable toxicities, patient refusal of further protocol therapy or for a maximum of 2 years after their first dose of study agent. Participants may also be removed if in the investigator's medical judgment, further participation would be injurious to the health and well being of the patient, or is not in the best interest of the patient.

The reason for study removal and the date the participant was removed must be documented in the source documentation and the study-specific case report form (CRF). The participant's status is to be modified in the MIDAS system once the participant completes the study.

Efforts will be made to obtain an autopsy on patients who die. Careful evaluation of potential target organs for toxicity will be made.

5.11 Supportive Care, Other Concomitant Therapy, Prohibited Medications

Participants will receive supportive care as clinically appropriate. This includes red cell and platelet transfusion support, antibiotics, antifungals and antiviral agents and agents for prophylaxis and management of tumor lysis. Hydroxyurea may be used at the treating physician's discretion during Cycle 1 of the Phase I (dose escalation) part of the protocol in order to control blood counts. Leukapheresis is permitted during Cycle 1 of Phase I to manage symptomatic leukostasis. All patients will receive oral metoprolol 25mg twice daily starting the day before initiation of Cycle 1 until 24 hours after completion of therapy.

Prohibited therapies from Cycle 1 Day 1 until 30-days post-last dose: Other anti-neoplastic therapies, agents that prolong or suspected to prolong QTc, and other investigational agents.

Patients must be instructed not to take any additional medications (including over-the-counter products) during the trial without prior consultation with the investigator. All medications taken within 28 days of planned start of treatment should be recorded. If concomitant therapy must be added or changed, the reason and name of the drug/therapy should be recorded.

5.12 Additional Studies

See Section 9.0 for correlative studies.

6.0 ANTICIPATED TOXICITIES, START OF CYCLE CRITERIA, AND DOSE DELAYS/MODIFICATIONS

6.1 Toxicities to 8-Chloro-adenosine

6.1.1 Expected (known) toxicities to 8-chloro-adenosine

To date no toxicities have been attributed to 8-chloro-adenosine in humans.

6.1.2 Possible anticipated toxicities to 8-chloro-adenosine

Events seen in chronic lymphocytic leukemia patients regardless of attribution that were at least two grades over baseline are listed with the highest grade indicated:

Hematologic: anemia (G3), neutropenia (G4), thrombocytopenia (G3)

Gastrointestinal: abdominal pain (G3), diarrhea (G2),

Metabolic: hypercalcemia (G4), hyperglycemia (G3), hypouricemia (G2),

General/Other: back pain (G3), fever (G2), sunburn (G2), flu syndrome (G2)

Toxicities seen in animal studies (murine and canine) using a range of regimens and doses (Section 2.5) are as follows:

Hematologic: transient thrombocytopenia

Gastrointestinal: vomiting

Renal: elevated BUN, renal nephrosis

General/Other: decreased activity, sloughing of the skin, dyspnea

Toxicities which may be foreseeable based on toxicities seen with other adenosine analogues (Cladribine, Didanosine, Fludarabine, Tenofovir) include the following (note: the asterisk indicates extremely rare but serious events):

Hematologic: thrombocytopenia, neutropenia, anemia, myelosuppression, pancytopenia*

Dermatologic: pruritus, rash, Stevens-Johnson syndrome*, toxic epidermal necrolysis*

Gastrointestinal: vomiting, nausea, diarrhea, abdominal pain, mucositis, stomatitis, anorexia, increased serum amylase, pancreatitis

Hepatic: increased liver enzymes, liver failure*

Metabolic: hyperuricemia

Musculoskeletal: arthralgia, myalgia, bone pain, backache, muscle weakness

Neurologic: headache, peripheral neuropathy, dizziness, insomnia

Renal: increased serum creatinine, renal failure*

Other: anaphylactoid reaction*, alopecia, fatigue, fever, chills, infection, pain, dyspnea, edema, diaphoresis, phlebitis

6.2 Start of Cycle Criteria:

Hematologic toxicities:

- For participants with CR, all hematologic toxicities must resolve to ≤ Grade 2
- For participants without CR, hematologic toxicity maybe of any grade.

Non-hematologic toxicities:

- Non-hematologic toxicities related to study agent must resolve to ≤ Grade 2.
- Non-hematologic toxicities not considered related to study agent may delay of start of cycle criteria per the discretion of the treating investigator.

For holds due to toxicities related to study agent, if the participant does not meet criteria to resume treatment by Day 49 from start of cycle, the participant must permanently discontinue study treatment. See Section 6.3 for dose modifications due to toxicity.

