6.3.2 Dose Modifications and Treatment Interruptions

The table below details the specific dose modifications and treatment interruptions for administration of 8-chloro-adenosine; they are to be used in agreement with the information in Section 6.3.1. Unless listed in Table 6.3.2, treatment will continue without interruption or dose modification. Start of cycle criteria will apply to initiate a new cycle of therapy (Section 6.2).

Table 6.3.2 Dose Modifications and Interruptions to 8-Chloro-adenosine Administration*

Adverse Event	Treatment Modification
Non-Hematologic toxicities considered RELATED to 8-chloro-adenosine in all participants:	
Grade 3 toxicity except for the following: 
 • vomiting, nausea, diarrhea that responds to maximum medical therapy • electrolyte imbalance, fatigue, anorexia, asthenia, stomatitis, mucositis, infection, dermatitis 	Hold study treatment until resolution to \leq Grade 2. Resume at pre-hold dose.
Grade 4 toxicity:	Hold study treatment until resolution to \leq Grade 2. Resume at 1 dose level reduction unless the toxicity is a grade 4 electrolyte imbalance correctable within 48 hours or grade 4 vomiting that responds to maximum medical therapy within 48 hours. In such cases patients can resume treatment at the assigned dose without reduction at the Physician's discretion.
Hematologic toxicity RELATED to 8-chloro Adenosine	
Grade \geq 3 peripheral blood cytopenia not resolving to \leq Grade 2 by day 49 from start of cycle in patients who have less than 5% bone marrow blasts	No additional cycles of study drug will be administered
Other unspecified Non-Hematologic Toxicities considered UNRELATED to study agent	
Other unspecified events of any grade considered unlikely or not related to study agent.	Maintain treatment with study agent. Interruption of study treatment is permitted if the investigator consults with the Principal Investigator to determine that this is in the best interest of the participant.

*: See section 5.2 for additional criteria to resume, make up missed doses.

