10.0 STUDY CALENDAR

Table 10 describes required procedures. All procedures may increase in frequency if clinically indicated.

Cycle length will be 28 days (+/-1 day), unless (a) there is a hold in treatment at Day 1, at which time the previous cycle will be extended until treatment is ready to resume on Day 1 of the subsequent cycle or (b) Day 1 assessments have yet to be reviewed for administering Day 1 agent, at which time the previous cycle will be extended until assessments are reviewed.

The day count continues despite a hold or delay in agent administration. Should a hold or delay in treatment occur, evaluations required by the protocol will be conducted at the original times during the cycle, even if agent(s) is not administered.

The Start of Cycle criteria are found in Section 6.2; **Day 1 treatments may not begin until the respective results of the Day 1 procedures are reviewed.** Windows for procedures follow in the table footnotes.

Table 10.0 Study Activity Calendar

	Pre-Study ^a	Cycles 1-4 ^{b,c}					30-day post last dose ^g	Active Follow-up ^h	Survival Follow-up ⁱ
		Day 1 ^d	Day 2-5 ^e	Day 8 ^f	Day 15 ^f	Day 22 ^f			
Informed consent ^j	X								
Medical history ^k	X								
Concurrent meds ^l	X	X		X	X	X	X		
Physical exam	X	X		X	X	X	X		
Vital signs ^m	X	X		X	X	X	X		
ECOG Performance Status ⁿ	X	X					X		
Adverse Event Evaluation ^o			-----X-----				X		
12 lead EKG	X	X ^p	X ^p						
Urinalysis	X	X					X		
B-HCG serum ^q	X								
CBC with diff + platelet count ^r	X	X	X	X	X	X	X		
Chemistry / metabolic panel ^s	X	X	X	X	X	X	X		
Bone Marrow Biopsy	X ^t					X ^{t,u}			
Response Assessment ^v						X ^v		X ^v	
Cardiac monitoring (telemetry unit)		X ^b	X ^b						
8-chloro-adenosine Infusion ^w		X	X						
Research blood collection	XX	X ^y	X ^y						
Research urine collection ^z		X							
Inclusion/Exclusion Criteria ^{aa}	X								
Registration ^{bb}	X								
Other anti-cancer treatment							X ^{cc}	X ^{dd}	
Survival ^{ee}							X	X	

- a. Pre-study procedures to be performed within 14 days of start of treatment.
- b. **Participants will be hospitalized during treatment administration (at minimum during the first six days of the cycle). Patients will undergo continuous cardiac monitoring in telemetry unit from start of treatment until 24 hours after completion of treatment during Cycles 1-4.**

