12.2 Response

The primary endpoint is complete remission rate (CR + CRi) and is based on the Döhner, 2010 criteria²⁴; calculated as the percent of evaluable patients that have confirmed CR or CRi.

Response criteria will be as follows:

CR: Bone marrow with < 5% blasts by morphology. ANC > 10³/µL, platelets ≥ 10⁵/µL

CRi: Bone marrow with < 5% blasts by morphology, not meeting blood count criteria for CR.

PR: Decrease of at 50% in bone marrow blasts

PD: Bone marrow blasts more than 20% and increase in blasts by over 50%.

HR: improvement in hematologic parameters, but not meeting criteria for PR.

Secondary activity endpoints for this study are as follows:

- Duration of response, defined as the time interval from the date of first documented response (CR+CRi) to documented disease relapse or death whichever occurs first.
- Overall survival, defined as the time interval from date of first dose of study drug to date of death from any cause.
- Event-free survival, defined as the time interval from date of first dose of study drug to first documented disease progression or death from any cause, whichever occurs first.
- Overall response rate (CR/CRI/PR), calculated as the percent of evaluable patients that have confirmed CR or CRi or PR.

12.3 Clinical Pharmacology Endpoints:

- For plasma PK, levels of 8-chloro-adenosine, its deaminated metabolite, 8-chloro-inosine, and its base 8-chloro-adenine will be quantitated in plasma during 5 days of therapy.
- For cellular PK, concentrations of 8-chloro-adenosine and 8-chloro-ATP will be quantitated in circulating leukemia cells in the peripheral blood.
- For urine PK, levels of 8-chloro-adenosine, its deaminated metabolite, 8-chloro-inosine, and its base 8-chloro-adenine will be quantitated in urine during the first 24 hours of therapy.
- For PD, the impact of therapy on endogenous ATP pools, as well as the effect on short-lived mRNA transcripts and proteins will be analyzed in circulating acute leukemia blasts.

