13.2 Definition of Dose-Limiting Toxicity (DLT)/Moderate Toxicity

With Amendment v09: A two level toxicity attribution scale will be used. In terms of attribution, all recorded adverse events will be classified as either related or unrelated to the study drug. Prior to this amendment a five level attribution scale (definite, possible, probable, unlikely, unrelated) was used.

A DLT will be defined as any of the following toxicities that occur during cycle 1, per CTCAE version 4.03, and are considered related to the study drug:

(Note: All adverse events will be considered relevant to determining dose-limiting toxicities and reporting unless the event can clearly be determined to be unrelated to the drug.)

Hematologic toxicities:

- For participants with less than 5% bone marrow blasts by morphology, with the exception of Grade 4 neutropenia, Grade 3 or 4 hematologic toxicity that does not resolve to Grade 2 by Day 49 (21 days after the day 28 cycle).
- For participants with less than 5% bone marrow blasts by morphology, Grade 4 neutropenia (absolute neutrophil count $<0.5 \times 10^9/L$) persisting up to Day 42 after the start of treatment.

Non-Hematologic toxicities:

- Any grade ≥ 3 non-hematologic toxicity for ≥ 7 days, with the exception of nausea not controlled by medical management within 72 hours.
- Any treatment related toxicity that prevents the administration of 80% of 8-chloro-adenosine during the first cycle of therapy.
- Delay in start of cycle 2 by more than 14 days due to drug-related non-hematologic toxicity.

Moderate toxicity will be defined as any grade 2 non-hematologic toxicity and occurs during cycle 1, per CTCAE v4.03, with the exception of:

- Allergic rhinitis
- Fatigue
- Sweating
- Weight gain or loss
- Alopecia
- Dry skin
- Nail or pigmentation changes
- Pruritus
- Hot flashes
- Flatulence
- Mouth dryness
- Nausea and vomiting without the use of maximal anti-emetic treatment
- Sense of smell or taste disturbance
- Erectile impotence
- Irregular menses
- Libido
- Oligospermia
- Tumor lysis syndrome
- Electrolyte/metabolic toxicity unable to be corrected within 48 hours
- Other grade 2 toxicity may be excluded pending PI and Data Safety Monitoring Committee (DSMC) review and approval

(Note: All adverse events will be considered relevant to determining moderate toxicities and reporting unless the event can clearly be determined to be unrelated to the drug.)

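### Section 6.2 ties count recovery before the next cycle to CR, but the hematologic DLTs and the Day 49 stop use under 5% marrow blasts, so a CRi participant with drug-related Grade 4 neutropenia may be re-dosed 13 days before the Day 42 read

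*Combined protocol and SAP*

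**What the plan says.** **Start of the next cycle (Section 6.2).** Participants with CR must have every hematologic toxicity at Grade 2 or lower. For everyone else: "For participants without CR, hematologic toxicity maybe of any grade".

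**Response categories (Section 12.2).** CR needs under 5% marrow blasts, ANC above 1000/µL and platelets of at least 100,000/µL. CRi is a separate category: "CRi: Bone marrow with < 5% blasts by morphology, not meeting blood count criteria for CR".

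**Hematologic DLTs (Section 13.2).** Both apply to participants with under 5% marrow blasts, whether or not CR is reached, and both must be related to study drug and occur during cycle 1. Grade 4 neutropenia counts if "persisting up to Day 42 after the start of treatment". Other Grade 3 or 4 hematologic toxicity counts if it has not come down to Grade 2 by Day 49. Events are treated as relevant "unless the event can clearly be determined to be unrelated to the drug".

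**Stop rule (Table 6.3.2).** Drug-related cytopenia of Grade 3 or higher ends study treatment if it has not come down to Grade 2 or lower "by day 49 from start of cycle in patients who have less than 5% bone marrow blasts". The table has no earlier hematologic hold, and the text above it says: "Unless listed in Table 6.3.2, treatment will continue without interruption or dose modification". It then refers the start of a new cycle back to Section 6.2.

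**The concern.** The recovery rule and the DLT and stop rules define their populations differently, and CRi falls between them: inside the DLT and stop rules, outside the recovery rule. The Day 42 DLT is aimed at participants whose marrow has cleared but whose neutrophils have not returned. Section 6.2 sets no wait for exactly those participants.

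Two things are at stake. First, if cycle 2 starts before the read, a neutropenia that began in cycle 1 may persist to Day 42 or Day 49 because of cycle 2 drug and still be scored as a cycle 1 DLT. Section 13.2 counts events unless they are clearly unrelated to the drug, so over-counting is the likely direction. That protects participants when the MTD is chosen but can end escalation too soon, and Section 13.6 uses the same DLT definition for unacceptable toxicity in phase II. Second, the participant may receive another five-day course with a cleared marrow and ANC below 500/µL, before the Day 49 rule can act.

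**Working it through.** **1. Check the plan's own figure.** Section 13.2 describes Day 49 as 21 days beyond the 28-day cycle: 28 + 21 = 49. It reproduces.

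**2. Who is covered.**
- Grade 4 neutropenia is ANC below 0.5 × 10^9/L = 500/µL (Section 13.2). CR needs ANC above 1000/µL (Section 12.2). The two cannot hold at the same assessment.
- A participant with under 5% blasts and Grade 4 neutropenia is therefore CRi. Sections 13.2 and Table 6.3.2 cover this participant if the cytopenia is drug-related. The recovery requirement in Section 6.2 does not.

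**3. Earliest re-dosing against the reads.** Inputs: cycle length 28 days ± 1 (Section 10.0); +7 day window for starting cycles 2-4 (calendar footnote c); five daily doses (Section 5.5); reads on Days 42 and 49 (Section 13.2). Nominal cycle 2 Day 1 is 28 + 1 = Day 29. The earliest is 27 + 1 = Day 28. The latest is 29 + 7 = Day 36, or Day 37 if the +1 and +7 windows are combined. The last cycle 2 dose is start + 4.

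| Cycle 2 start | Days to Day 42 | Days to Day 49 | Last cycle 2 dose | Last dose to Day 42 | Last dose to Day 49 |
|---|---|---|---|---|---|
| Day 28 | 14 | 21 | Day 32 | 10 | 17 |
| Day 29 (nominal) | 13 | 20 | Day 33 | 9 | 16 |
| Day 36 | 6 | 13 | Day 40 | 2 | 9 |
| Day 37 | 5 | 12 | Day 41 | 1 | 8 |

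For a Day 29 start the reads fall on cycle 2 Day 42 − 29 + 1 = 14 and Day 49 − 29 + 1 = 21. If Day 42 is taken as 42 elapsed days, the nominal gap is 14 rather than 13. In every row all five cycle 2 doses precede both reads.

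**4. Does other text impose a wait?**
- Section 5.2: if there is a hold or delay, "after the last dose is administered in a given cycle, there will be a 21 day break". Suppose one hold covers Days 2-4 and dosing resumes on Day 5. Doses 2-5 fall on Days 5-8, the break is Days 9-29, and cycle 2 may start on Day 30, still 42 − 30 = 12 days before Day 42.
- Section 10.0: for a treatment hold at Day 1, "at which time the previous cycle will be extended until treatment is ready to resume on Day 1 of the subsequent cycle". This keeps the reads inside cycle 1 for a held participant but does not create the hold.
- The Day 49 limits in Sections 6.2 and 6.3.1 apply to participants already on hold.
- Calendar footnote v says the end-of-cycle-1 response does not decide whether a participant goes on to cycle 2.

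None of these makes a CRi participant wait for counts.

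**5. What one over-counted DLT does (Section 13.3).** 0 of 3 (escalate) becomes 1 of 3 (expand); 1 of 3 (expand) becomes 2 of 3 (cease); 1 of 6 (continue) becomes 2 of 6 (cease). The documents give no rate for CRi or for persistent cytopenia, so no probability can be attached.

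**The case against.** The strongest reply is that CR in Section 6.2 is shorthand for a cleared marrow. The primary endpoint, the complete remission rate, pools CR and CRi. On the strict reading the recovery bullet does little for neutrophils or platelets, because CR already requires good counts. The Day 49 limit on holds also matches the Day 49 DLT and stop rule, which suggests that waiting was intended. This may well be the intent. But Section 12.2 separates the categories, and Sections 12.2 and 13.1 name both when both are meant, so staff who follow Section 6.2 as written need not hold a CRi participant.

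Three stronger readings are tempting, and the documents do not support them:
- *That the plan directs re-dosing.* It only permits it. Day 1 results are reviewed before dosing (Section 10.0), and Section 5.7 lets the investigator stop treatment.
- *That a cytopenia first caused by cycle 2 drug becomes a cycle 1 DLT.* Section 13.2 limits DLTs to toxicities occurring during cycle 1. Only prolongation of a cytopenia already present in cycle 1 is at issue. The clearly-unrelated note concerns attribution to the drug and does not override that limit.
- *That every cytopenia with a cleared marrow is covered.* The DLTs and the Table 6.3.2 row require a relationship to study drug.

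It also stands that the chain is narrow. The marrow must clear after one cycle, severe cytopenia must remain at about Day 29, and dosing must go ahead after review. For the miscount, the counts would also have had to recover in time without cycle 2. In phase II the consequence under Section 13.6 is an accrual halt and committee review, not automatic termination.

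**Conclusion.** The inconsistency is real on the text. As written, a CRi participant with drug-related Grade 4 neutropenia may start cycle 2 at nominal Day 29, 13 days before the Day 42 read and 20 days before the Day 49 read (5-14 and 12-21 days across the stated windows). The effect on dose-finding is possible over-counting of cycle 1 DLTs through prolonged cytopenia, a conservative error of unknown and probably low frequency. The effect on the participant is a possible further five-day course before a rule that might have ended treatment.

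This rests on reading CR in Section 6.2 as Section 12.2 defines it. If shorthand was meant, the same edit records the intent. Severity is minor to should-fix: the exposure is narrow, but the rule works against the plan's own DLT and stop rules and is cheap to align.

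**What to change.** - **Section 6.2.** Replace the CR group by *participants with <5% bone marrow blasts (CR or CRi)*, and the group without CR by *participants with ≥5% bone marrow blasts, or whose marrow was skipped for rising blood blasts* (the exception in calendar footnote u).
- **Relatedness.** For CRi, limit the recovery requirement to hematologic toxicity not clearly unrelated to study drug, matching Table 6.3.2 and Section 13.2. Without this limit, CRi participants with unrelated cytopenia would be held too, for example after transplant or with AML evolving from MDS.
- **Section 13.2.** Add one sentence: in participants with <5% blasts, cycle 2 is not started while a potential hematologic DLT from cycle 1 is unresolved. Both reads then precede any re-dosing of those participants.

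**Cost.** Two wording changes. The marrow is already allowed on Days 22-28 (calendar footnote f), so blast status can be known in time, although result turnaround is not stated. A held participant needs counts to Day 42 or 49, which the DLT read already requires.

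**Downside.** A few CRi participants start cycle 2 later or stop at Day 49. They remain evaluable for response under Section 13.1, which accepts CR or CRi after one cycle. However, the Synopsis (Phase II Design) counts phase I patients treated at the RP2D toward the 25 only after at least two cycles, so one who stops could be lost from that count.
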